**Table 4: Schedule of Assessments – Part B**

Study Activity	Visit	Treatment Period								ET o	Follow-up p 4±1
		VB1	VB2	VB3	VB4	VB5	VB6	VB7	VB8		
	Week	Day 1	4±1	12±1	20±1	28±1	36±1	44±1	52±1		
ELIGIBILITY ASSESSMENTS											
Informed Consent		X a									
Concomitant medications b			X	X	X	X	X	X	X	X	X
Vital signs c and weight d			X	X	X	X	X	X	X	X	X
Full physical examination e									X	X	
Brief physical examination f			X	X	X	X	X	X			X
Contraceptive assessment g and record LMP for WOCBP h			X	X	X	X	X	X	X	X	X
Urine β HCG for WOCBP			X	X	X	X	X	X	X	X	X
SAFETY ASSESSMENTS											
AE monitoring			X	X	X	X	X	X	X	X	X
12 lead ECG i						X			X	X	
STUDY PRODUCT ADMINISTRATION											
Dispense study product j		X	X	X	X	X	X	X			
Collect and count capsules of returned study product			X	X	X	X	X	X	X	X	
PATIENT-REPORTED EFFICACY ASSESSMENTSk											
PtGA			X	X	X	X	X	X	X	X	
HAQ-DI			X	X	X	X	X	X	X	X	
SF-36			X	X	X	X	X	X	X	X	
PROMIS-29 Short Form			X	X	X	X	X	X	X	X	
Patient VAS score for pain			X	X	X	X	X	X	X	X	
FACIT-Fatigue Score			X	X	X	X	X	X	X	X	
5-D Itch Questionnaire			X	X	X	X	X	X	X	X	
Skindex-29+3			X	X	X	X	X	X	X	X	
EQ-5D questionnaire			X	X	X	X	X	X	X	X	
PHYSICIAN ASSESSMENTS OF EFFICACYl											
MMT-8			X	X	X	X	X	X	X	X	
CDASI score			X	X	X	X	X	X	X	X	
IGA scale of skin activity			X	X	X	X	X	X	X	X	
EMGA (10 cm VAS)			X	X	X	X	X	X	X	X	
MDGA (10-cm VAS and Likert Scale)			X	X	X	X	X	X	X	X	

Study Activity	Visit	Treatment Period								ET o	Follow-up p 4±1
		VB1	VB2	VB3	VB4	VB5	VB6	VB7	VB8		
	Week	Day 1	4±1	12±1	20±1	28±1	36±1	44±1	52±1		
LABORATORY ASSESSMENTS											
CBC with differential and platelets			X		X		X		X	X	X
Metabolic panel (includes ALT, AST and LDH) m			X		X		X		X	X	X
CK and aldolase			X		X		X		X	X	
Blood biomarkers						X			X	X	
Autoantibody measurements									X	X	
Urine dipstick n			X		X		X		X	X	
ADDITIONAL ASSESSMENTS											
Spirometry				X		X		X		X	X

a Subjects who rollover into Part B should sign an ICF by or before Visit 10 in Part A. If OLE is extended beyond 1 year, ICF for the extended OLE should be signed by or before Visit B8

b Doses of immunosuppressive medications (including corticosteroids) should be assessed and may be reduced as specified in [Section 5.5.1](#) at every study visit along with all other concomitant medications.

c Systolic and diastolic BP will be measured with the subject supine for at least 5 minutes. The same arm should be used for the measurement throughout the study as much as possible. Pulse and respiration will also be measured with the subject supine for at least 5 minutes. Body temperature will be measured on the skin or in the mouth.

d Weight will be measured with coats, jacket, and footwear removed.

e Full physical examination includes the following assessments alertness and orientation, general appearance, skin, head, eyes, ears, nose, and throat, lungs, heart, abdomen, musculoskeletal examination, and lymph nodes. Breast and genitourinary examinations are not required.

f Brief physical examination includes the following assessments: skin, lung, heart, abdomen, and any other area as indicated by changes in medical history.

g Applicable for women ≤ 55 years of age with no menses for ≥ 1 year.

h Refer to [Appendix 1](#) for the criteria for determining reproductive potential and acceptable methods of contraception.

i 12-lead ECG with QT/QTc intervals should be recorded with the subject in a rested supine position ≥ 10 minutes before the test.

j Study product will be dispensed for administration in women of childbearing potential only if urine pregnancy test is negative.

k Ideally, all patient-reported efficacy assessments should be completed before all other study procedures, in the order listed.

l It is preferred that physician assessments of efficacy are performed in the order listed.

m Metabolic panel includes glucose, urea nitrogen, creatinine, estimated glomerular filtration rate, blood urea nitrogen/creatinine, sodium, potassium, chloride, carbon dioxide, calcium, protein total, albumin, bilirubin total, alkaline phosphatase, aspartate aminotransferase (AST), alanine aminotransferase (ALT), lactate dehydrogenase (LDH); AST, ALT and LDH are three of the five muscle enzymes comprising the TIS (see [Section 8.1.2](#)).

n Urine dipstick for blood, protein, glucose

o Subjects who discontinue the study at any stage, and for any reason, will be encouraged to complete the procedures described in the Early Termination (ET) Visit

p The Safety Follow-up Visit is to occur 4±1 weeks after the last visit (VB8 unless OLE is extended beyond 1 year); discontinued subjects will be encouraged to complete this visit 4±1 weeks after the ET Visit.

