Blood biomarkers			X					X				X	X	
Blood for flow cytometry (at selected sites)			X					X				X	X	
Paxgene tube collection			X									X	X	
Autoantibody measurements			X									X	X	
Urine dipstick			X	X				X				X	X	
PHARMACOKINETIC ASSESSMENTS														
Lenabasum plasma concentration and metabolite profiling			X	X		X		X				X	X	
ADDITIONAL ASSESSMENTS														
Spirometry		X	X			X		X				X	X	
Skin biopsies (optional at selected sites)			X			X						X	X	
Skin photography (optional at selected sites)			X									X	X	
Patient Improvement Questionnaire for Subjects						X		X				X	X	
Patient Improvement Questionnaire for Physicians						X		X				X	X	

a Must fulfill Bohan and Peter's criteria for probable or definite DM or ACR/EULAR criteria for DM

b Medical history includes the following: subject demographic information, history and disease manifestations of DM including ILD, concurrent illnesses and past, smoking history (packyears) classified into one of the following categories: current smoker; ever smoked (>= 1 cigarette/day for > 1 year); never smoked, and any other relevant medical history.

c Doses of immunosuppressive medications (including corticosteroids) should be assessed at every study visit along with all other concomitant medications.

d Systolic and diastolic BP will be measured with the subject supine for at least 5 minutes. The same arm should be used for the measurement throughout the study as much as possible. Pulse and respiration will also be measured with the subject supine for at least 5 minutes. Body temperature will be measured on the skin or in the mouth.

e Weight will be measured with coats, jacket, and footwear removed.

f Standing height will be measured with footwear removed.

g Full physical examination includes the following assessments: alertness and orientation, general appearance, skin, head, eyes, ears, nose, and throat, lungs, heart, abdomen, musculoskeletal examination, and lymph nodes. Breast and genitourinary examinations are not required.

h Brief physical examination includes the following assessments: skin, lung, heart, abdomen, and any other area as indicated by changes in medical history.

i Applicable for women  $\leq$  55 years of age with no menses for  $\geq$  1 year.

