### 7.2.2.2. Visit B2, Visit B4, and Visit B6 (Weeks 4, 20, and 36)

- Patient-reported efficacy assessments
  - PtGA
  - HAQ-DI
  - SF-36
  - PROMIS-29 Short Form
  - Patient VAS score for pain
  - FACIT-Fatigue Score
  - 5-D Itch Questionnaire
  - Skindex-29+3

---

 Subjects who rollover into Part B should sign an ICF by Visit 10 in Part A and preferably earlier than Visit 10, if possible.

- EQ-5D questionnaire
- Collect and count capsules of returned study product
- Record concomitant medication(s)
- AE monitoring
- Contraceptive assessment and record of LMP for WOCBP
- Vital signs (including BP, pulse rate, respiratory rate, and temperature) and weight
- Spirometry
- Brief physical examination
- Physician assessments of efficacy
  - MMT-8
  - CDASI score
  - IGA scale of skin activity
  - EMGA (10-cm VAS)
  - MDGA (10-cm VAS and Likert Scale)
- Laboratory tests
  - CBC with differential cell count and platelets
  - Metabolic panel (includes ALT, AST, and LDH)
  - CK and aldolase
  - Urine  $\beta$ hCG in WOCBP
  - Urine dipstick
- Dispense study product

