### **8.2. Safety Assessments**

#### **8.2.1. Medical History and Use of Contraception**

Medical history will include subject demographics, history of DM and current treatment for DM. The medical history also will include concurrent illnesses, other current medications, past relevant medical history, smoking history (classified as one of the following: current smoker, ever smoker (defined as  $\geq 1$  cigarette per day for  $> 1$  year), or never smoker), child-bearing potential, last menstrual period (LMP) for women, and review of systems. Date of LMP and method of contraception will be assessed at screening and all visits in WOCBP.

Acceptable contraceptive methods (as stated in [Appendix 1](#)), may not be available or approved in all countries; thus, the Sponsor does not restrict respective countries from excluding unavailable contraceptive methods in the ICF.

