## APPENDIX 1. REPRODUCTIVE POTENTIAL AND ACCEPTABLE METHODS OF CONTRACEPTION

Women are considered to have “no childbearing potential” if they meet any of the following criteria:

- Hysterectomy
- Bilateral oophorectomy
- Bilateral tubal ligation
- Post-menopausal; menopause is defined as no menses for 12 months without an alternative medical cause, not using hormone contraception or hormonal replacement therapy. In women  $\leq$  55 years of age with no menses for  $\geq$  12 months, FSH and LH levels should be measured to confirm postmenopausal state.

Acceptable methods of contraception must be used by subjects who are women of child-bearing potential or their male sexual partners. Acceptable methods of contraception must be used by subjects who are male or their female sexual partners of child-bearing potential.

Acceptable and highly effective methods of contraception are those that result in a low failure rate (i.e., less than 1 percent per year) when used consistently and correctly. Examples of highly effective methods of contraception when used consistently and correctly include:

- Combined (estrogen and progesterone containing) hormonal contraception associated with inhibition of ovulation
  - Oral
  - Intravaginal
  - Transdermal
- Progesterone-only hormonal contraception associated with inhibition of ovulation
  - Oral
  - Injectable
  - Implantable
- Intrauterine device
- Intrauterine hormone-releasing system
- Bilateral tubal occlusion
- Vasectomized partner
- Sexual abstinence. Abstinence is only acceptable when this is the preferred and usual lifestyle of the individual. Periodic abstinence (calendar, symptothermal, post-ovulation methods), withdrawal (coitus interruptus) and lactational amenorrhea method are not acceptable means of contraception.

[figure not shown]
Another acceptable method of contraception that is allowed in the study is:

Combination of condom and spermicide

---

 Acceptable contraceptive methods may not be available or approved in all countries; thus, the Sponsor does not restrict respective countries from excluding unavailable contraceptive methods in the ICF.

[figure not shown]

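### Table 4 footnote g limits the Part B contraceptive assessment to women aged 55 or younger with no menses for at least a year, contradicting its own row label, the visit lists and Section 8.2.1

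*Protocol*

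**What the plan says.** Table 4 (Section 7.1) schedules one combined row at VB2 to VB8, early termination and follow-up. With its markers the row reads "Contraceptive assessment g and record LMP for WOCBP h". Marker g therefore sits on the contraceptive assessment and marker h on WOCBP.

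- Footnote g: "Applicable for women ≤ 55 years of age with no menses for ≥ 1 year".
- Footnote h refers to Appendix 1 "for the criteria for determining reproductive potential and acceptable methods of contraception".

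The text describes the same procedure differently. Section 7.2.2.2 (B2, B4, B6) lists "Contraceptive assessment and record of LMP for WOCBP", and the same entry stands in Section 7.2.2.3 (B3, B5, B7), Section 7.2.2.4 (B8 or early termination) and Section 7.2.3 (Safety Follow-up). None of these adds a condition on age or menses. Section 8.2.1 gives a general rule: "Date of LMP and method of contraception will be assessed at screening and all visits in WOCBP".

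Appendix 1 defines menopause as "no menses for 12 months without an alternative medical cause" in women not using hormonal contraception or replacement. For women of 55 or younger with that history it asks for FSH and LH to confirm the postmenopausal state.

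**The concern.** A schedule table is what many sites work from at a visit, and Section 8 sends the reader to it for planned time points. Here its footnote selects a group that Appendix 1 treats as possibly postmenopausal, pending hormone tests, and leaves out women who have menstruated within the past year. The row label, the visit lists and Section 8.2.1 name WOCBP. A site cannot follow the footnote and these other passages together.

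At stake is a safety procedure. Every Part B subject receives lenabasum 20 mg BID. Section 8.2.7.8 says the effect in pregnancy is unknown, and inclusion criterion 10 requires WOCBP to be willing to continue contraception until at least 4 weeks after stopping study product. The contraceptive assessment is the scheduled check on that commitment. Under Section 3.1.2 an extended open-label period follows the design and procedures of Table 4, so the conflict would carry into visits C1 to C8.

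**Working it through.** No sample size, power or error rate bears on this point, so there is nothing to calculate beyond a count of visits. The check sets the passages side by side.

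1. **Whom each place names for the contraceptive assessment in Part B**
   - Table 4 row label: WOCBP.
   - Table 4 footnote g, on the same row: women of 55 or younger with no menses for at least 1 year.
   - Sections 7.2.2.2, 7.2.2.3, 7.2.2.4 and 7.2.3: WOCBP, no further limit.
   - Section 8.2.1: WOCBP, at screening and all visits.

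   Footnote g stands alone against its own row label and five sections.

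2. **Whom the footnote selects.** Appendix 1 attaches the same age and menses condition to one purpose, deciding whose FSH and LH are measured. Women confirmed postmenopausal have no childbearing potential. Some women in the footnote group may still be WOCBP, for example where the absence of menses has another medical cause. Combined with the row label, the footnote would leave only that narrow group to be assessed.

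3. **Where the sentence probably came from.** Table 3 (Part A) has the same condition in its footnote i ("55 years of age with no menses for"), followed by footnote j, which points to Appendix 1. Table 3 has an FSH and LH row just above its contraceptive row. Table 4 has the same two footnotes in the same order, as g and h, but no FSH/LH row. The Table 3 markers are not visible in the text available, so transfer from the FSH/LH row is an inference. It fits the order of rows and notes and the use of the condition in Appendix 1.

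4. **Whether the marker is a reading error.** Table 4's markers run in order from a to p, and the neighbouring ones fit their rows: e full examination, f brief examination, i ECG, j dispensing. Misreading of g is unlikely.

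5. **Extent on a literal reading.** Seven treatment visits (VB2 to VB8), early termination and follow-up make 7 + 1 + 1 = 9 scheduled columns, plus the extension visits if the open-label phase is prolonged.

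6. **What footnote g leaves alone.** LMP recording carries only marker h. Table 4 schedules the urine pregnancy test for WOCBP at the same nine columns, and footnote j makes dispensing to WOCBP conditional on a negative result.

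**The case against.** The strongest reply is that the governing rule is already clear. Section 8.2.1 states it outright, Section 7.2 refers to Section 8.2 for the detailed description of procedures, and the visit lists agree. The row also contradicts itself: it asks for LMP in WOCBP while marker g confines the other half to women with no menses for a year. Site staff may well see the mistake and query it.

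Most of this stands. It shows that the footnote is the outlier and that its practical effect may be small. It does not remove the conflict: I found no statement of whether table or text prevails, Section 8 points back to the schedule, and the extension is defined by reference to Table 4.

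Three stronger readings are tempting, and the documents do not support them.

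- **That women in Part B would go without pregnancy monitoring.** The urine test and the dispensing condition are outside footnote g, as are the pregnancy stopping and reporting provisions in Section 8.2.7.8. Section 7.2.2.3 does not itself list the urine test at B3, B5 and B7, but that is a separate discrepancy. A pregnancy test is also no substitute for a contraception check, since it detects a pregnancy that has already begun.
- **That sites would in fact skip the assessment.** That follows only if staff read the footnote literally and disregard the label, footnote h, the lists and Section 8.2.1.
- **That about two-thirds of subjects are affected.** Section 4.6 gives a roughly 2:1 female-to-male prevalence ratio and says only that more women than men are expected. It does not forecast enrolment. Nor does it say how many of the women menstruate, and Section 1.2 puts the most common age of onset at 50 to 60 years.

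**Conclusion.** The contradiction is real and lies within an operative safety schedule. Table 4 footnote g names a different population for the contraceptive assessment from its own row label, Sections 7.2.2.2 to 7.2.2.4, Section 7.2.3 and Section 8.2.1. It is probably a misplaced footnote.

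On a literal reading the loss is confined to one procedure, the scheduled contraception check in women who still menstruate, at the nine Table 4 columns and any extension visits. The number of women cannot be given from the protocol. No endpoint, efficacy analysis, sample size or type I error is touched. The conclusion rests on the marker placement in Table 4, which is legible. The account of how the footnote arose is an inference, and the conclusion does not depend on it.

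**What to change.** Reconcile Table 4 footnote g with the row label, the Part B and Safety Follow-up visit lists, Section 8.2.1 and Appendix 1, so that every place names the same population for the contraceptive assessment. Which population that is remains for the sponsor's clinical and safety staff to confirm. Then remove the footnote, or reassign it if there is a Part B procedure to which it belongs. Check the corrected table before it is used for an extended open-label period.

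The cost is one footnote, in the next amendment or a clarification letter to sites. No analysis changes.

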## 7.2. Study Visits

A detailed description of all study procedures is provided in [Section 8.2](#). Ideally, all patient-reported efficacy assessments should be completed before all other study procedures, in the order listed. It is preferred that physician assessments of efficacy are performed in the order listed.

### 7.2.1. Part A

#### 7.2.1.1. Screening (up to 4 weeks before Visit 1)

- Informed consent
- Patient-reported efficacy assessments, with instruction/ training in instrument by study staff
  - PtGA
  - HAQ-DI
  - SF-36
  - PROMIS-29 Short Form
  - Patient VAS score for pain
  - FACIT-Fatigue Score
  - 5-D Itch Questionnaire
  - Skindex-29+3
  - EQ-5D questionnaire
- Medical history (including a detailed history of DM)
- Record concomitant medication(s)
- AE monitoring
- Contraceptive assessment and record of last menstrual period (LMP) for WOCBP
- Height, which will be used throughout trial as Baseline
- Vital signs (including blood pressure [BP], pulse rate, respiratory rate, and temperature) and weight
- 12 lead ECG
- Spirometry for FVC
- Full physical examination
- Physician assessments of efficacy
  - MMT-8
  - CDASI score

- IGA scale of skin activity
- EMGA (10-cm VAS)
- MDGA (10-cm VAS and Likert Scale)
- Physician assessment of DM activity (see [Appendix 5](#))
- Laboratory tests:
  - HIV, HBV and HCV testing
  - FSH and LH (if applicable)
  - Serum  $\beta$  HCG for WOCBP
  - Complete blood count (CBC) with differential and platelets
  - Metabolic panel (includes ALT, AST, and LDH)
  - Creatine phosphokinase (CK) and aldolase
- Verify eligibility criteria (including verification of DM)

#### 7.2.1.2. Randomization

Randomization within IWRS will occur before or at Visit 1. The subject does not need to be present in clinic for randomization to occur. See [Section 5.3](#) for additional details.

#### 7.2.1.3. Visit 1 (Day 1)

##### Pre-dose:

- Verify eligibility criteria (including verification of DM)
- Patient-reported efficacy assessments
  - PtGA
  - HAQ-DI
  - SF-36
  - PROMIS-29 Short Form
  - Patient VAS score for pain
  - FACIT-Fatigue Score
  - 5-D Itch Questionnaire
  - Skindex-29+3
  - EQ-5D questionnaire
- Record concomitant medication(s)
- AE monitoring
- Contraceptive assessment and record of LMP for WOCBP

- Vital signs (including BP, pulse rate, respiratory rate, and temperature) and weight
- 12 lead ECG
- Spirometry for FVC
- Full physical examination
- Physician assessments of efficacy
  - MMT-8
  - CDASI score
  - IGA scale of skin activity
  - EMGA (10-cm VAS)
  - MDGA (10-cm VAS and Likert Scale)
- Laboratory tests
  - CBC with differential cell count and platelets
  - Metabolic panel (includes ALT, AST and LDH)
  - CK and aldolase
  - Blood biomarkers
  - Blood for flow cytometry (optional at selected sites)
  - Paxgene tube collection
  - Autoantibody measurements
  - Urine  $\beta$ hCG in WOCBP
  - Urine dipstick
- Skin biopsies (optional at selected sites)
- Skin photography (optional at selected sites)
- Lenabasum plasma concentration and metabolite profiling
- Dispense study product

**Dosing:**

- The first dose of study product will be administered in the clinic using dispensed study product.

**Post-dose (3  $\pm$  0.5 hrs)**

- Vital signs (including BP, pulse rate, respiratory rate, and temperature)
- 12 lead ECG
- Lenabasum plasma concentration and metabolite profiling

#### 7.2.1.4. Visit 2 (Week 4 ± 1)

- Every effort should be made to remind the subject of dosing requirements for PK sampling ([Section 5.1](#)) 1-3 days prior to the scheduled visit
- Patient-reported efficacy assessments
  - PtGA
  - HAQ-DI
  - SF-36
  - PROMIS-29 Short Form
  - Patient VAS score for pain
  - FACIT-Fatigue Score
  - 5-D Itch Questionnaire
  - Skindex-29+3
  - EQ-5D questionnaire
- Collect and count capsules of returned study product
- Record concomitant medication(s)
- AE monitoring
- Contraceptive assessment and record of LMP for WOCBP
- Vital signs (including BP, pulse rate, respiratory rate, and temperature) and weight
- 12 lead ECG
- Brief physical examination
- Physician assessments of efficacy
  - MMT-8
  - CDASI score
  - IGA scale of skin activity
  - EMGA (10-cm VAS)
  - MDGA (10-cm VAS and Likert Scale)
- Laboratory tests
  - CBC with differential cell count and platelets
  - Metabolic panel (includes ALT, AST and LDH)
  - CK and aldolase
  - Urine  $\beta$ hCG in WOCBP

- Urine dipstick
- Lenabasum plasma concentration and metabolite profiling
- Dispense study product

**7.2.1.5. Visit 3, Visit 5, Visit 7, Visit 9 (Weeks 10, 22, 34, and 46)**

- Collect and count capsules of returned study product
- Record concomitant medication(s)
- AE monitoring
- Contraceptive assessment and record of LMP for WOCBP
- Vital signs (including BP, pulse rate, respiratory rate, and temperature) and weight
- Brief physical examination
- Laboratory tests
  - CBC with differential cell count and platelets
  - Metabolic panel (includes ALT, AST and LDH)
  - Urine βhCG in WOCBP
- Dispense study product

**7.2.1.6. Visit 4 (Week 16 ± 1)**

- Every effort should be made to remind the subject of dosing requirements for PK sampling ([Section 5.1](#)) 1-3 days prior to the scheduled visit
- Patient-reported efficacy assessments
  - PtGA
  - HAQ-DI
  - SF-36
  - PROMIS-29 Short Form
  - Patient VAS score for pain
  - FACIT-Fatigue Score
  - 5-D Itch Questionnaire
  - Skindex-29+3
  - EQ-5D questionnaire
- Patient Improvement Questionnaire for Subjects (see [Appendix 4](#))

---

 Study personnel will be required to contact subjects 3±1 weeks after Visit 9 to assess compliance and safety.

- Collect and count capsules of returned study product
- Record concomitant medication(s)
- AE monitoring
- Contraceptive assessment and record of LMP for WOCBP
- Vital signs (including BP, pulse rate, respiratory rate, and temperature) and weight
- Spirometry
- Brief physical examination
- Physician assessments of efficacy
  - MMT-8
  - CDASI score
  - IGA scale of skin activity
  - EMGA (10-cm VAS)
  - MDGA (10-cm VAS and Likert Scale)
- Patient Improvement Questionnaire for Physicians (see [Appendix 3](#))
- Laboratory tests
  - CBC with differential cell count and platelets
  - Metabolic panel (includes ALT, AST, and LDH)
  - CK and aldolase
  - Urine  $\beta$ hCG in WOCBP
- Skin biopsies (optional at selected sites)
- Lenabasum plasma concentration and metabolite profiling
- Dispense study product

